STATISTICS Primary Analysis Plan	
Aims 1 and 2: Global assessment of intervention effects will be evaluated using a two-sided t-test or Wilcoxon rank sum test if normality of the measurement is questionable (as determined by QQ-normal plots). Further analysis will quantify effects of patient age, BMI and other body composition measures on change in fasting glucose using linear regression. Differential effects between intervention and control arms will be quantified using interaction terms. All analyses will compare effects based on intention-to-treat.
 
Aim 3: Global assessment of intervention effects will be evaluated using a two-sided t-test (or Wilcoxon rank sum test). Linear regression will be used to assess associations of IR, IGF-1R, and AKT expression with systemic measures of glycemic control at 6 months.
 
Aim 4: We will follow the DPP research group characterization of sustained weight loss as maintenance of a 7% reduction in weight and sustained glucose regulation as maintenance within 5% of 6-month levels. Because not all participants will achieve 7% weight loss at 6 months, we will look in the subset of participants who did and did not achieve this goal both separately and combined. A one-sample test of proportions will be used to determine whether the proportion of participants that are able to sustain lifestyle changes differs from zero.

Rationale for Number of Subjects	Our power calculations give the minimally detectable intervention effects for endpoints in Primary Specific Aims, setting two-sided alpha error at 5% and power at 80%. We have set a sample size of 100 in each of the intervention and control arms, based both on our overall evaluation of minimum detectable differences across the range of study endpoints and on a reasonable estimate of the number of men we can recruit. The sample size allows for a drop-out rate of 5%, and power calculations assume correlations of 0.70 between baseline and follow-up measures.

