#### **1.4 Diabetes Prevention Program**

The DPP studied over 3,000 participants with elevated fasting glucose levels randomized to metformin, a 6-month lifestyle modification program or placebo. The goal of the lifestyle modification program was a 7% reduction in body weight through a structured dietary program and at least 150 minutes of weekly physical activity. The lifestyle intervention decreased incident diabetes mellitus (DM) by 58% vs. controls, while metformin reduced incident DM by 31%. Fasting glucose declined from a mean of 107 to 101 mg/dl in the lifestyle group whereas no change was seen in the placebo group. Long term follow-up of the DPP has demonstrated sustained weight loss at 10 years, which is an important consideration as other studies of dietary interventions in men with PCa have used diets that are difficult to maintain over the long-term (e.g., vegan, low glycemic and prepared meals). The results of the lifestyle intervention have also been found to be cost-effective and cost saving. A meta-analysis of weight loss studies based on the DPP lifestyle modification program consistently shows statistically significant and clinically relevant reductions in weight; however, the majority of participants in those studies were women and no studies to date have been conducted in older men with cancer. Despite this, there are indications that older men may be an ideal population for the DPP lifestyle intervention. Older participants ( $\geq 60$  years) compared to younger groups (25-44 yrs. and 45-59 yrs.), had the greatest weight loss (mean -6.4 kg vs. -4.1 and -5.0 kg respectively,  $p < 0.001$ ) and more commonly met the exercise goal (48% vs. 34% and 38% respectively,  $p < 0.001$ ). The lifestyle intervention was more effective than metformin at weight loss with increasing age ( $p = 0.005$ ). In addition, compared to women, men lost more weight ( $p < 0.01$ ) and performed higher levels of physical activity ( $p < 0.05$ ) in the lifestyle intervention. However, since only 20% of participants were older than 60 years of age, fewer than 1/3 of participants were men, and none of the participants had cancer, whether these results will have similar effects in a PCa population are unknown, but certainly these data provide evidence that the DPP intervention can succeed in this population. Thus, the DPP intervention offers a novel strategy to improve PCa patient outcomes and yield insights on biological pathways by which obesity may delay or prevent disease progression.

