## 5 CRITERIA FOR EVALUATION

### 5.1 Primary Endpoint

The primary endpoints for each of the primary aims are:

**Primary Aim 1:** change in fasting glucose levels relative to baseline between the intervention and control arms.

**Primary Aim 2:** change in fasting C-peptide, insulin, IGF-1, IGF-BP3, and adiponectin levels relative to baseline between the intervention and control arms.

**Primary Aim 3:** change in expression of IR, IGF-1R, and AKT on prostate cancer epithelial cells from follow-up surveillance biopsy (6 months post-randomization) relative to 'baseline' (biopsy ~6 months prior to randomization).

**Primary Aim 4:** will test whether PCa patients randomized to the intervention arm are able to sustain the beneficial changes in weight and glucose regulation an additional 6 months after the active intervention.

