## **11 STATISTICAL METHODS AND CONSIDERATIONS**

**Primary Aim 1.** The primary analysis will compare change in fasting glucose level relative to baseline between the intervention and control arms. Global assessment of intervention effects will be evaluated using a two-sided t-test or Wilcoxon rank sum test if normality of the measurement is questionable (as determined by QQ-normal plots). Further analysis will quantify effects of patient age, BMI and other body composition measures on change in fasting glucose using linear regression. Differential effects between intervention and control arms will be quantified using interaction terms. All analyses will compare effects based on intention-to-treat.

**Primary Aim 2.** Additional analyses will compare changes in levels of C-peptide, insulin, IGF-1, IGF-BP3, and adiponectin relative to baseline measurements between the intervention and control arms. As in Aim 1, we will compare global and subgroup effects based on intention-to-treat analyses.

**Primary Aim 3.** We will test whether the change in expression of IR, IGF-1R, and AKT on prostate cancer epithelial cells from follow-up surveillance biopsy (6 months post-randomization) relative to 'baseline' (biopsy ~6 months prior to randomization, see Fig. 3) differs between intervention and control arms. Global assessment of intervention effects will be evaluated using a two-sided t-test (or Wilcoxon rank sum test). Linear regression will be used to assess associations of IR, IGF-1R, and AKT expression with systemic measures of glycemic control at 6 months. Exploratory analyses will also evaluate associations between adverse pathology, biomarkers of glycemic control and IR/IGF-1R/AKT expression.

**Primary Aim 4.** We will test whether PCa patients randomized to the intervention arm are able to sustain the beneficial changes in weight and glucose regulation an additional 6 months after the active intervention. We will follow the DPP research group characterization of sustained weight loss as maintenance of a 7% reduction in weight and sustained glucose regulation as maintenance within 5% of 6-month levels. Because not all participants will achieve 7% weight loss at 6 months, we will look in the subset of participants who did and did not achieve this goal both separately and combined. A one-sample test of proportions will be used to determine whether the proportion of participants that are able to sustain lifestyle changes differs from zero.

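### Primary Aim 4's only weight criterion, a fixed 7% loss, cannot show maintenance in men below 7% at month 6, so the combined proportion mixes reaching the goal with keeping it

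*Combined protocol and SAP*

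**What the plan says.** Section 5.1 states the Aim 4 question as whether intervention-arm men "are able to sustain the beneficial changes in weight and glucose regulation an additional 6 months after the active intervention". Section 7.5 assigns the evaluation of maintenance to month 12.

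Section 11 (Primary Aim 4) defines success on two outcomes in one sentence, with different reference points:

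- Weight: "sustained weight loss as maintenance of a 7% reduction in weight", a fixed threshold. The synopsis repeats it ("characterization of sustained weight loss as maintenance of a 7% reduction in weight").
- Glucose: "sustained glucose regulation as maintenance within 5% of 6-month levels", which is relative to each man's own month-6 value.

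The plan foresees men below the threshold ("Because not all participants will achieve 7% weight loss at 6 months") and responds that "we will look in the subset of participants who did and did not achieve this goal both separately and combined". The planned test asks whether "the proportion of participants that are able to sustain lifestyle changes differs from zero". No separate weight criterion is given for men below 7% at month 6, none of the three analysis sets is named as primary, and no power or expected proportion is given for Aim 4.

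**The concern.** The question is about change from month 6 to month 12. The weight rule looks at the level reached at month 12, measured from baseline. For a man who passed 7% at month 6 the two are related, since he either still meets the goal or does not. For a man who did not, they come apart. He can keep every kilogram of his loss and be counted as not sustaining it, or he can be counted as sustaining a 7% loss that he did not have when the intervention ended.

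Such men are likely to be common, as the plan concedes. The combined proportion then depends on how many men reached 7% as well as on how many kept their loss, and a reader could not separate the two. Aim 4 is one of four primary aims. With three analysis sets and none named as primary, the choice among three quite different proportions could be made after the data are seen.

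**Working it through.** The plan gives no figure for Aim 4 to reproduce (Table 4 covers Aims 1 to 3), so the check applies the stated rule to simple cases and then to an assumed distribution.

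**Reading of the rule.** Success = loss from baseline at month 12 of at least 7%. Section 11 does not spell out the reference point or the inequality. Section 7.4 sets the 7% goal as a share of total body weight to be lost over the 6-month programme, so baseline is the natural reference.

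**Individual cases** (baseline weight = 100)

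| Loss at month 6 | Loss at month 12 | Share of loss kept | 7% rule |
|---|---|---|---|
| 6.9% | 6.9% | 100% | fails |
| 5% | 5% | 100% | fails |
| 3% | 7.5% | new loss | passes |
| 10% | 7.0% | 70% | passes |
| 14% | 7.0% | 50% | passes, exactly on the line |
| 14% | 6.86% | 49% | fails |

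The first three rows are non-achievers. In that subset a pass always means further loss after month 6.

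**How common are non-achievers?** Section 1.4 reports that the oldest participants in the diabetes prevention trial "had the greatest weight loss (mean -6.4 kg vs. -4.1 and -5.0 kg respectively"). A loss of 6.4 kg equals 7% at a baseline weight of 6.4 / 0.07 = 91.4 kg; above that weight, the same loss falls short of 7%. On an assumed 95 kg it is 6.4 / 95 = 6.7%.

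**Group figures.** Assumptions, none of them from the documents except the 6.4 kg: 6-month loss is normal with mean m = 6.7% and SD s = 5 points, and every man keeps the same share k of his loss. A man then passes if k × loss ≥ 7, that is, if loss ≥ 7/k.

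- Combined proportion = 1 − Φ((7/k − m)/s).
- Achiever proportion = combined proportion divided by its value at k = 1.
- Non-achiever proportion = 0 for any k ≤ 1.

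| Share kept, k | Threshold 7/k | z = (7/k − 6.7)/5 | Combined | Achievers | Non-achievers |
|---|---|---|---|---|---|
| 1.00 | 7.00 | 0.060 | 47.6% | 100% | 0% |
| 0.75 | 9.33 | 0.527 | 29.9% | 62.8% | 0% |
| 0.50 | 14.00 | 1.460 | 7.2% | 15.2% | 0% |

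**Sensitivity**

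- Perfect maintenance (k = 1), m = 6.7: 47.0% at SD 4 and 48.0% at SD 6.
- Perfect maintenance, m = 5, SD 5: z = (7 − 5)/5 = 0.40, giving 34%.
- A quarter regained (k = 0.75), m = 6.7: combined 25.5% at SD 4 and 33.0% at SD 6; achievers 54.3% and 68.8%.

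So a trial in which no man regains anything would report a combined sustained proportion of about one third to one half, set by how many reached the goal.

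**The case against.** Much can be said for the plan.

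*The achiever analysis is sound.* A reader might infer that the 7% rule cannot measure maintenance at all. The documents do not support that. Section 11 plans a separate analysis of men who reached 7%, and still being at least 7% below baseline is a coherent measure of holding the goal. Its limit is that regain stopping above the line goes unseen. Nor is it right that men below 7% have nothing to maintain: a man with a 6.9% loss has a loss to keep, but not a 7% one.

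*The combined figure does respond to regain.* It falls from 48% to 30% to 7% as the share kept falls from all to three quarters to half. So it is not merely a count of early achievers, and it does not stay high when regain is large. The case of a 14% loss half regained passes only by sitting exactly on the line.

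*The plan may not intend the 7% rule for non-achievers.* It says only that they will be looked at, and the glucose criterion does apply to them. That is fair, but no other weight criterion is stated. If the 7% rule is not meant for them, their success on weight is undefined.

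*Late attainment is a purpose of the programme.* Section 7.4 provides monthly newsletters in months 6 to 12 to help men reach or keep their goal. That justifies reporting goal attainment at month 12, but not calling it sustained loss.

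*The definition is attributed to the diabetes prevention research group.* A fixed goal is a legitimate choice for describing attainment. Precedent does not make it answer a question about change after month 6.

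*The test result would not change.* Proportions of 48% and 30% would both be declared different from zero. This stands: the harm is to the reported proportion and its meaning. Whether zero is a useful null value is a separate matter.

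**Conclusion.** The concern holds for the non-achiever and combined analyses. In non-achievers the only stated weight criterion cannot show maintenance, and in the combined set it mixes reaching 7% with keeping it. Under the assumed mean of 6.7% and SD of 5 points, the combined proportion is 48% with no regain by anyone, and 34% if the mean is 5%. With a quarter of each loss regained it is 30% (25.5% to 33.0% for SDs of 4 to 6).

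The mechanism follows from the wording. The percentages rest on an assumed baseline weight of 95 kg, assumed SDs, normality, uniform proportional regain, and the reading of the rule as at least 7% below baseline at month 12. The achiever analysis stands as a measure of holding the goal. This should be fixed, though it does not threaten the data or the planned test's conclusion.

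**What to change.** In Section 11 (Primary Aim 4) and the matching synopsis entry:

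1. Anchor weight maintenance to each man's own 6-month weight, as is already done for glucose. Make the Aim 4 weight result the mean percent weight change from month 6 to month 12 in the intervention arm, with its 95% CI.
2. Show it beside the mean change from baseline to month 6. Otherwise men who lost nothing and stayed level would look like successful maintainers.
3. If a retained share is wanted, use the ratio of the arm means. The mean of individual ratios is unstable when a man's 6-month loss is near zero.
4. Restrict the sustained-7% proportion to men who reached 7% at month 6.
5. Report the proportion at least 7% below baseline at month 12 in all intervention men separately, labelled goal attainment, and state the reference weight and the inequality.
6. Name one primary analysis set.

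The cost is rewording only: Section 7.5 already schedules weight at baseline, 6 and 12 months. The downside is that a single sustained/not-sustained proportion is no longer the headline weight result. The interval in step 1 also does not by itself give a yes/no verdict; if one is wanted, the team must set its margin before the data are seen.

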## 4 STUDY DESIGN

### 4.1 Study Overview

This will be a 6-month, prospective, randomized trial in overweight ( $BMI = 25-29 \text{ kg/m}^2$ ) and obese ( $BMI \geq 30 \text{ kg/m}^2$ ) men with PCa ( $n=200$ ) who have elected AS. Patients will be randomized to either:

1. Lifestyle intervention (a structured diet and exercise program based on the DPP); or
2. Control (oral and written information based on general U.S. dietary and physical activity guidelines).

Following randomization, men will be followed for 12 months, and the 12 month start and end dates will coincide with the yearly prostate biopsies that are part of routine clinical care for AS patients (thus no extra biopsies will be performed solely for the study; Fig. 3). Baseline and post-intervention (at 6 and 12 months) measures of glucose regulation will be compared along with BMI, physical activity, caloric intake, additional insulin related biomarkers, function and quality of life and pathologic endpoints.

Month 0	1	2	Month 3	4	5	Month 6	7	8	9	10	11	Month 12									
PALS STUDY VISIT TIMELINE																					
CLINIC VISIT 1				CLINIC VISIT 2				CLINIC VISIT 3				CLINIC VISIT 4									

 
• Informed Consent
 
• Blood draw
 
• Height/weight
 
• Waist/hip measures
 
• Questionnaires
 
• DXA scan
 
• Exercise test
 
• Meet with Nutritionist
 
	
 
• Blood draw
 
• Weight
 
• Waist/hip measures
 
• Questionnaires
 
			
 
• Blood draw
 
• Weight
 
• Waist/hip measures
 
• Questionnaires
 
• Exercise test
 
			
 
• Blood draw
 
• Weight
 
• Waist/hip measures
 
• Questionnaires
 
• DXA scan
 
			
 
• Tissue collection
 
											
PALS Lifestyle Intervention group only																					
PALS Sessions 
 
• Up to 11 one-on-one healthy eating instruction sessions
 
• Up to 24 supervised exercise sessions
 
							
 
• Maintenance of healthy eating and physical activity
 
														

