Compliance. Compliance to dietary and physical activity goals will be evaluated both formally and informally. The primary formal tool to assess overall study compliance will be participant weight loss; weight will be measured at each session (using a research scale and a standardized protocol) and if participants are meeting weight loss goals then compliance is achieved. Other formal compliance tools to assess compliance will include study dietitian-directed proactive check-ins and completion of a 3-day diet record (at 6 mo). At each intervention session the dietitian will review progress and any potential barriers, and individual dietary goals will be adjusted as needed. Formal measures for adherence to physical activity goals will include reviewing heart rate monitor data and formal check-ins with the exercise physiologist. Informally, compliance to diet, physical activity and weight loss goals will be assessed by self-monitoring through logs and journaling. In addition, global-study wide tailored messages with diet, physical activity and behavioral strategies content will be delivered by text message and e-blasts. This multi-tiered approach has been shown to maximize adherence and retention during intervention trials.

**Controls.** Written information on standard healthy lifestyle recommendations will be provided along with a 20-30 minutes individual session with a dietitian including 1) US Dietary Guidelines ([www.dietaryguidelines.gov](http://www.dietaryguidelines.gov)); 2) Activity goal of 30 minutes of physical activity 5 days/week; and 3) Discussion of the health benefits of weight loss along with general behavior change suggestions for weight loss.

Follow-up Visits. All participants will come to the Fred Hutch Cancer Prevention Center for study visits at baseline (0), 3, 6 and 12 months. A description of the clinical assessments performed at each follow-up visit is provided below.

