## 7.5 Clinical Assessments

Study visits will occur at baseline, 3, 6 and 12 months. During study visits, participants will undergo anthropometrics, fasting blood studies and/or complete physical activity, food diaries and HRQOL questionnaires. Assessments at 6 months will be used to evaluate the effectiveness of the intervention, and at 12 months will evaluate maintenance of the intervention.

Anthropometric Measurements. Height will be measured at baseline only, and weight, waist (1" above umbilicus), hip circumferences will be measured at baseline, 3, 6 and 12 months. Dual x-ray absorptiometry (DXA) using a GE Lunar iDXA will be obtained to measure overall percent body fat, lean mass and total bone density at baseline and 12 months.

Twelve-hour fasting blood. Fasting blood samples will be collected at baseline, and at 3, 6, and 12 months. Vacutainers will be labeled with participants' study ID and date, processed within 1 hour of collection and stored at -70°C.

Prostate Tissue. As part of the consent to participate in this study, participants are asked to give permission to investigators to allow a) the collection of two extra prostate biopsy cores during their standard-of-care biopsy (UW and VA participants only), and b) access to pathology tissue from a pre-study biopsy (that was already collected as part of routine medical care for diagnostic purposes) to be used for this study (UW and VA participants only). For VA patients, separate consent allowing the collection of extra biopsy cores during a standard-of-care biopsy, and allowing access to biopsy tissue after used for diagnostic purposes will be obtained at the VAPSHCS by VA study staff on the day of their scheduled biopsy. For participants who are not patients at UW or the VA, since the collection of extra biopsy cores is not possible, they will be asked to sign a separate "Release of Information" allowing access to prostate biopsy tissue collected as part of their routine care. Tissue blocks, fixed in formalin and embedded in paraffin (standard for AS biopsies), will be sent to [name] laboratory. Participants will be enrolled on study so that the intervention calendar coincides with routine clinical care; no extra biopsies will take place outside of the routine clinical care. Tissue blocks will be cut and sections mounted on charged slides.

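### Primary Aim 4 tests the intervention-arm proportion who sustain their changes against zero, so a significant result cannot show that the 6-month benefit was kept

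*Combined protocol and SAP*

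**What the plan says.** Section 11, Primary Aim 4, and the matching Synopsis entry (Primary Analysis Plan, Aim 4) ask whether men in the intervention arm hold on to their gains in weight and glucose regulation for six months after the programme ends. The test is there to "determine whether the proportion of participants that are able to sustain lifestyle changes differs from zero".

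Two per-man definitions are given. For weight, a 7% reduction must be maintained. For glucose, the plan defines "sustained glucose regulation as maintenance within 5% of 6-month levels". It does not say whether a man must meet one or both, or whether the 5% band runs in both directions. Results are to be looked at in men who did and did not reach 7% loss at 6 months, separately and together.

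Section 3.1 lists Aim 4 among the primary aims. Table 4 in Section 11.1 covers Aims 1 to 3 only, so Aim 4 has no expected rate, success threshold or power.

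Two other passages touch month 12. Section 4.1 says "Baseline and post-intervention (at 6 and 12 months) measures of glucose regulation will be compared along with BMI", and Section 7.5 says assessments "at 12 months will evaluate maintenance of the intervention". Neither names a test or a between-arm contrast for Aim 4. By contrast, Aim 1 is explicit: "The primary analysis will compare change in fasting glucose level relative to baseline between the intervention and control arms".

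**The concern.** A test against a proportion of zero asks whether anyone at all succeeded. The aim asks whether the changes were sustained. The first can be answered yes when nearly all of the benefit has gone.

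The glucose definition adds to this. It is anchored to each man's own 6-month value, so a man whose glucose never improved can count as sustained. So can many men in an arm whose mean effect has vanished, because ordinary within-man variation leaves a good share of them near their 6-month reading.

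At stake is the conclusion on a primary aim. Followed as written, the plan can yield a significant p-value that invites the statement that lifestyle changes were sustained, when it establishes only that the proportion is not nil.

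**Working it through.** The plan gives no Aim 4 figure to reproduce.

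**Inputs**
- n = 100 × 0.95 = 95 intervention men (Section 11.1: 100 per arm, 5% drop-out).
- Fasting glucose SD 12.6 mg/dL (Table 4).
- Means of 101 and 107 mg/dL. Section 1.4 reports of the earlier diabetes-prevention trial: "Fasting glucose declined from a mean of 107 to 101 mg/dl in the lifestyle group". Month 6 is set at 101, and month 12 at 101 (effect kept) or 107 (effect fully lost).
- Correlation r between months 6 and 12: not given. Section 11.1 assumes 0.70 between baseline and follow-up; I use that with a range of 0.40 to 0.90.
- Normality is assumed.

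**The null of zero**
- Exact test: if p = 0 then P(X ≥ 1) = 0, so 1 of 95 (1.1%) rejects.
- z test with null variance: 0 × (1 − 0)/95 = 0, so the statistic is undefined.
- Wald z = p̂ / √(p̂(1 − p̂)/95). For 3/95, 0.0316/0.0179 = 1.76 (not significant). For 4/95, 0.0421/0.0206 = 2.04 (significant).

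**Glucose tested on its own**

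SD of the 6-to-12-month change = 12.6 × √(2(1 − r)) = 13.80, 9.76 and 5.63 at r = 0.40, 0.70 and 0.90.

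Hand approximation at r = 0.70, taking the band as 5% of 101 = 5.05 mg/dL:
- Kept: upper limit Φ(5.05/9.76) = 0.698; two-sided 2 × 0.698 − 1 = 0.395.
- Lost (mean rise 6): upper limit Φ((5.05 − 6)/9.76) = 0.461; two-sided 0.461 − Φ(−11.05/9.76) = 0.461 − 0.129 = 0.332.

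Simulation (3 million pairs, band = 5% of each man's own 6-month value):

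| r | Two-sided: kept / lost | Only a rise fails: kept / lost |
|---|---|---|
| 0.40 | 29% / 27% | 64% / 47% |
| 0.70 | 39% / 34% | 69% / 46% |
| 0.90 | 63% / 41% | 81% / 44% |

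The lowest rate in the table is 26.7% before rounding. With 95 men, the chance of three or fewer successes at that rate is 1.1 × 10⁻⁹. Every scenario therefore rejects almost surely, kept or lost, by the exact or the Wald test.

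**Weight alone, or weight and glucose together**

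The documents give no rate of 7% loss at month 12, so these are illustrations only.
- Weight alone at 1%, 2% or 5%: exact rejection 1 − (1 − p)⁹⁵ = 62%, 85%, 99%; Wald P(X ≥ 4) = 2%, 12%, 71%.
- Joint success, assuming independence, glucose at 34% to 39% and weight at 5%, 10% or 20%: exact 80–85%, 96–98%, over 99%; Wald 8–12%, 41–51%, 89–94%.

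Rejection is not assured on these readings, but its meaning does not change: it still takes only one to four men.

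**What a month-12 between-arm contrast would show**

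Baseline-adjusted SE of the glucose difference = 12.6 × √(1 − r²) × √(2/95), with r here between baseline and month 12: 1.31 at 0.70 and 1.68 at 0.40. The smallest significant difference is 1.96 × SE = 2.6 and 3.3 mg/dL. If half of a 6 mg/dL effect remains, power is 63% and 43%.

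**The case against.** The best defence is that Aim 4 is a within-arm question wherever it appears (Synopsis, Sections 3.1, 5.1 and 11), so a missing control contrast is a design choice. That stands: the error is the null, and the lack of a control arm in this test is not a fault in itself.

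It can also be said that the observed proportion will be visible to readers and can be informative. That stands in part. The plan speaks of beneficial changes, so a further fall in glucose would hardly count as failure. On that reading, or at high r, the proportion does separate kept from lost. A reader might infer that the maintenance proportion is worthless; the figures do not support that. It is the comparison with zero that tells nothing.

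The 7% and 5% figures are not a defence. They define success for one man and set no benchmark for the proportion. Splitting by 6-month achievement leaves the null at zero.

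A reader might also infer that the test must always reject. That holds for glucose on its own under the stated assumptions; on the other readings it depends on an unknown weight-loss rate.

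Finally, it is tempting to make a month-12 glucose comparison between arms the deciding test. The documents do not support that either. It would change the aim and demote weight, which Aim 4 names beside glucose. Nor could it show that the benefit was kept, since it can be significant with half the effect gone.

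**Conclusion.** The concern holds as a fault in the stated null and should be fixed. One success in 95 rejects exactly and four reject by Wald, so significance on this primary aim shows only that a few men met the definition. For glucose tested alone, rejection is near certain whether the mean effect is kept or fully lost, at every correlation from 0.40 to 0.90 and on both readings of the 5% band. This rests on normality, Table 4's SD and the earlier trial's means. The arithmetic on the null itself needs only n = 95. Nothing here touches Aims 1 to 3 or the sample size.

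**What to change.** Delete the test against zero in Section 11 and the Synopsis, and align the wording of Aim 4 in Sections 3.1 and 5.1 and the Synopsis, which now speaks of testing. Then:

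1. State whether sustained means weight, glucose or both, and whether the 5% band is upper-only.
2. Report for the intervention arm, with 95% confidence intervals, the maintenance proportions for weight and for glucose (overall and by whether 7% loss was reached at 6 months) and the mean 6-to-12-month changes in weight and glucose. Base the conclusion on these estimates. For mean glucose change the half-width is 1.986 × SD of change / √95, about 2.0 mg/dL at r = 0.70 and 2.8 at r = 0.40.
3. Add, as supporting analyses, baseline-adjusted intervention-versus-control differences at month 12 in weight and in fasting glucose, with 95% confidence intervals. Describe them as showing whether a between-arm difference persists, not that the 6-month effect was fully maintained.

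A benchmark proportion would also repair the null, but the documents offer no figure for one.

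The cost is text edits. Both arms already supply the data: "All participants will come to the Fred Hutch Cancer Prevention Center for study visits at baseline (0), 3, 6 and 12 months", Section 7.5 measures weight at month 12, and "Fasting blood samples will be collected at baseline, and at 3, 6, and 12 months". The downside is that Aim 4 no longer yields an easy significant result.

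Month-12 values may also be affected by drop-out or by cancer treatment after the follow-up biopsy. Section 11 places that biopsy 6 months after randomization, Section 11.1 expects adverse pathology in about 25% of men, and Section 1.3 notes that androgen deprivation can influence metabolic markers. The plan should say that this will be noted when the results are interpreted.
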